2.4.3 Extent of investigational medicinal product exposure and compliance

The extent of IMP exposure and compliance will be assessed and summarized by actual treatment within the safety population ([Section 2.3.2](#)).

2.4.3.1 Extent of investigational medicinal product exposure

The extent of IMP exposure will be assessed by the duration of IMP exposure.

Duration of IMP exposure is defined as last dose date – first dose date + 14 days, regardless of unplanned intermittent discontinuations (see [Section 2.5.3](#) for calculation in case of missing or incomplete data). Duration of IMP exposure will be summarized descriptively as a quantitative

variable (number, mean, SD, median, minimum, and maximum). In addition, duration of treatment exposure will also be summarized categorically by numbers and percentages for each of the following categories and cumulatively according to these categories:

- >0 and ≤ 2 weeks
- >2 and ≤ 4 weeks
- >4 and ≤ 8 weeks
- >8 and ≤ 12 weeks
- >12 and ≤ 16 weeks
- ...
-
- >48 and ≤ 52 weeks
- >52 weeks

Additionally, the cumulative duration of treatment exposure will be provided, defined as the sum of the duration of treatment exposure for all patients, and will be expressed in patient years.

2.4.3.2 Compliance

A given administration will be considered noncompliant if the patient did not take the planned dose of treatment as required by the protocol. No imputation will be made for patients with missing or incomplete data.

Percentage of compliance for a patient will be defined as the number of administrations that the patient was compliant divided by the total number of administrations that the patient was planned to take during the treatment epoch defined in [Section 2.1.4](#).

Treatment compliance percentages will be summarized descriptively as quantitative variables (number, mean, SD, median, minimum, and maximum). The percentage of patients whose compliance is $<80\%$ will be summarized in [Section 2.4.4.5](#).

Cases of overdose (defined as at least twice the intended dose during an interval of less than 11 days) will constitute serious adverse events and will be listed as such. More generally, dosing irregularities will be listed in [Section 2.2.1](#).

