#### **8.1.4 Dosing schedule**

Regardless of the treatment arm, all randomized patients will receive q2w SC administrations of either dupilumab or placebo on D1 (V2). For Arm B, after Week 24, dupilumab administration will be alternated by placebo matched injection every other week up to Week 50 (last investigational medicinal product [IMP] administration). Every other week IMP administrations must be separated by at least 11 days.

At V2, the Investigator (or delegate) will perform the injection. After V2, every other week administration of IMP will be performed at the investigational site up to at least Week 8 (V6). The IMP will be administered following clinic procedures and blood collection. Patients will be monitored at the study site for at least 30 minutes or minimum time required by your local regulator after injections for signs of hypersensitivity reaction.

From Week 10, every other week home administration of IMP (by patient, caregiver, or health care professional) is possible if the patient (or caregiver) has been trained for 4 injections. Training must be documented when completed successfully and training injections must be recorded in the source documents. When IMP is administered at home, the patients must be advised by the site staff to self-monitor for potential signs and symptoms that may suggest a hypersensitivity reaction for at least 30 minutes after administration or minimum time required by your local regulator. If the patient (or caregiver) is unable or unwilling to administer IMP, arrangements must be made for qualified site personnel and/or healthcare professionals to administer IMP for the doses not scheduled to be given at the study site. If the patient, or caregiver(s) do not develop the comfort to inject the investigational drug at home, or the Investigator determines that patient (or caregiver) injection at home is not appropriate, injections can be performed at the site by way of unscheduled visits.

Subcutaneous injection sites should be alternated among the 4 quadrants of the abdomen (avoiding navel and waist areas), the upper thighs or the upper arms, so that the same site is not injected twice consecutively. Injection in the upper arms could be done only by a trained person (caregiver trained by Investigator or Delegate) or health care professional but not the patients themselves.

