### **11.4.1.2 Compliance**

A given administration will be considered noncompliant if the patient did not take the planned dose of treatment as required by the protocol. No imputation will be made for patients with missing or incomplete data.

Percentage of compliance for a patient will be defined as the number of administrations the patient was compliant divided by the total number of administrations the patient was planned to take during the treatment period (ie, from the 1st to the last administration).

Treatment compliance, above-planned and under-planned dosing percentages will be summarized descriptively (N, Mean, SD, Median, Min, and Max). The percentage of patients with compliance is <80% will be summarized. In addition, number and percentage of patients with at least 1 above planned dosing administration will be given, as well as the number and percentage of patients with 0, (0, 20%], and >20% under-planned dosing administrations.

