1.5 MODIFICATIONS TO THE STATISTICAL SECTION OF THE PROTOCOL

There is no change from the statistical section of the protocol..

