2.1.4 Safety endpoints

The safety analysis will be based on the reported adverse events and other safety information, such as clinical laboratory data, vital signs, ECG and physical examination.

Observation period

The observation period will be divided into 4 epochs:

- The **screening** epoch is defined as the time from the signed informed consent date up to the time prior to first administration of the IMP.

- The **treatment** epoch is defined as the time from the first administration of the IMP to the last administration of the IMP + 14 days.
- The **residual treatment** epoch is defined as the time from the last administration of the IMP +15 days to the last administration of the IMP + 98 days.

The treatment-emergent adverse event period will include both **treatment** and **residual treatment** epochs.

- The **posttreatment** epoch is defined as the period of time starting the day after the end of the treatment-emergent adverse event period up to the end of the study (defined as last protocol planned visit or the resolution/stabilization of all serious adverse events and adverse events with pre-specified monitoring).
- The on-study observation period is defined as the time from start of treatment until the end of the study (defined as last protocol planned visit or lost to follow-up or the resolution/stabilization of all serious adverse events and adverse events with pre-specified monitoring).

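### The SAP's injection-compliance denominator runs 14 days past the last dose, unlike the protocol's, and read literally it can count one untaken dose against patients who stop early

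*SAP*

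**What the plan says.** Protocol 11.4.1.2 defines a patient's compliance as the compliant administrations over this count: "total number of administrations the patient was planned to take during the treatment period (ie, from the 1st to the last administration". The parenthesis closes there.

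SAP 2.4.3.2 keeps the numerator but changes the denominator to the "total number of administrations that the patient was planned to take during the treatment epoch defined in" SAP 2.1.4. On the treatment phase, that section reads: "epoch is defined as the time from the first administration of the IMP to the last administration of the IMP + 14 days". On the residual phase, it reads: "epoch is defined as the time from the last administration of the IMP +15 days to the last administration of the IMP + 98 days". Day +14 after the last injection therefore belongs to the treatment epoch.

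Both documents plan to report the percentage of patients whose compliance is under 80%. On departures from the protocol, SAP 1.5 states: "There is no change from the statistical section of the protocol".

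**The concern.** The two denominators do not cover the same span. The protocol stops counting at the last injection, while the SAP goes on for a further 14 days, which is exactly one dosing interval. For someone who stops early, the next scheduled injection can land on or just before the final day of the epoch. It would then enter the denominator as a dose not taken.

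If so, the compliance percentage mixes two things: how well patients followed the schedule while on treatment, and whether they stopped. Stopping is already reported under disposition (SAP 2.2). The mean and the share below 80% would also differ between arms whenever early stopping differs, even with identical adherence on treatment. The change is not declared in SAP 1.5.

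**Working it through.** The documents give no figure to reproduce here, so this is a direct count.

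**Inputs**
- Injections every 14 days in all arms, the last at Week 50 (Protocol 8.1.4). With Week 0 as Day 1, planned days are 1, 15, ..., 351, which is 26 doses.
- Planned dates run from the first injection, with a visit window of 3 days either way (Protocol 10.1). Injections must be at least 11 days apart (Protocol 8.1.4).
- SAP denominator: planned days on or before last dose day + 14 (SAP 2.4.3.2 with 2.1.4).
- Assumption: a scheduled dose still counts as planned after the patient has stopped. Neither document says.

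**Last dose on schedule, none missed.** After k doses the last is on day 1 + 14(k − 1). The epoch ends on day 1 + 14k, which is the planned day of dose k + 1. For k < 26, compliance = k/(k + 1).

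| Doses taken (k) | SAP, literal | Protocol |
|---|---|---|
| 1 | 1/2 = 50% | 100% |
| 2 | 2/3 = 66.7% | 100% |
| 3 | 3/4 = 75% | 100% |
| 4 | 4/5 = 80%, not below the cut-off | 100% |
| 5 | 5/6 = 83.3% | 100% |
| 13 | 13/14 = 92.9% | 100% |
| 25 | 25/26 = 96.2% | 100% |
| 26 (completer) | 26/26 = 100%, as no dose is planned at Week 52 | 100% |

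**Last dose off schedule.**
- Up to 3 days late: the epoch end moves later and still takes in exactly one further planned day, so the score stays k/(k + 1).
- 1 to 3 days early, k ≥ 2: the next planned day is 15 to 17 days after the last dose, outside the epoch, so the score is k/k = 100%.
- k = 1: the only dose is itself the anchor, so no offset is possible and the score is 50%.

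**Illustration of size.** Assume that 25% of 360 patients stop, spread evenly over the 12 dosing intervals to Week 24, and that none missed a dose before stopping. The 25% is borrowed from the dropout allowance in Protocol 11.1 and SAP 1.3.
- Stoppers: 0.25 × 360 = 90, or 90/12 = 7.5 per interval.
- On schedule, below 80% for k = 1, 2, 3: 3 × 7.5 = 22.5, about 22 patients (6.25%).
- Last-dose offset uniform on −3 to +3 days: 4 of the 7 values are on time or late, and this applies only to k = 2 and 3. 7.5 + 2 × 7.5 × 4/7 = 16.1, about 16 patients.
- Loss in mean compliance, on schedule: 0.25 × (1/12) × (1/2 + 1/3 + ... + 1/13) = 0.25 × 0.182 = 0.045, or 4.5 percentage points.
- With 10% stopping, on schedule: 0.10 × 3/12 × 360 = 9 patients, and 0.10 × 0.182 = 1.8 points.

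**The case against.** The best reply is that the denominator counts doses the patient was *planned to take*. Under Protocol 10.3.1, permanent discontinuation is a definitive decision not to give the drug again. Someone who has stopped is arguably no longer planned to take the next dose, and on that reading every row of the table is 100%. The reading also agrees with the protocol and with SAP 1.5. It cannot be ruled out, but the SAP does not state it. The SAP replaced the protocol's explicit first-to-last span with a dated window, and a programmer following the text would count scheduled dates in that window.

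The effect also depends on one boundary day. The +14 days is natural for exposure duration (SAP 2.4.3.1) and for daily spray compliance (SAP 2.4.2.1.1), and if day +14 were excluded an on-schedule stopper would score 100%. As written, the residual epoch starts at +15, so day +14 is included.

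A reader might infer that everyone who stops after one to three doses will be reported as below 80%. The documents do not support that, because a second or third and final dose given 1 to 3 days early yields 100%.

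Nor is each untaken dose at day +14 an artefact. Under Protocol 10.3.2, an interruption of more than 2 doses leads to permanent discontinuation. For such a patient the dose after the last injection was planned and missed, and the SAP's window captures that where the protocol's does not. This part of the objection stands.

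**Conclusion.** The discrepancy between protocol and SAP is plain on the text and undeclared. Its numerical effect is conditional: it needs the literal reading of the epoch, a dose due after discontinuation counted as planned, and a last injection on time or late. Under those conditions, full adherence followed by early stopping is scored as k/(k + 1), below the cut-off for one to three doses.

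The patient counts and the 4.5 points are illustrations only. The 25% is a sample-size allowance for dropout, not a forecast of how many will stop injections. The even timing, the absence of earlier missed doses and the uniform offset are all assumed.

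It would be tempting to infer that trial conclusions are at risk. They are not. IMP compliance is summarised descriptively in the safety population (SAP 2.4.3), efficacy is analysed by intention to treat, and no efficacy analysis uses the compliance percentage or the 80% cut-off. This is a minor point, worth correcting because it affects a prespecified reported figure.

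**What to change.** In SAP 2.4.3.2, define the denominator as the administrations planned from the first to the last administration of IMP, inclusive, and drop the reference to the treatment epoch. This restores the protocol's rule, makes SAP 1.5 true on this point and settles how doses due after stopping are treated. In the same edit, correct the cross-reference that sends the below-80% summary to SAP 2.4.4.5, which is the exploratory efficacy section.

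The cost is one sentence and no new data. There is a small downside: doses missed after the last injection but before formal discontinuation will not count as non-compliance. Treatment discontinuation (SAP 2.2) and exposure duration (SAP 2.4.3.1) are already reported separately, so early stopping itself remains visible.

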Detailed instructions for transport, storage, preparation, and administration of IMP are provided to the patient. For doses not given at the study site patients will complete a paper dosing diary to document compliance with self-injection (or caregiver) of IMP, location of injection, and any symptoms. The diary will be kept as source data in the patient's study file.

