### **8.7.1 Treatment accountability and compliance**

The Investigator or delegate will keep accurate records of the quantities of the IMP dispensed and returned, used and unused and NIMP dispensed and returned, used and unused by each patient.

- Proper recording of treatment kit numbers as required on appropriate electronic case report form (e-CRF) page for accounting purposes.
- All medication treatment kits (whether empty or unused) are returned by the patient at each visit when a treatment dispensing is planned and at EOT visit.
- The completed patient diary (returned to the site at each visit), returned IMP treatment and NIMP kit boxes used and unused along with any unused prefilled syringes will be used for drug accountability purposes. Patients will also return used prefilled syringes to the site in a sharp container.
- The Investigator (or designee) tracks treatment accountability/compliance by diary, and by counting the number of used and unused treatment kits and syringes and completes the appropriate page of the patient treatment log.
- The monitor in charge of the study then checks the data entered on the IMP and NIMP administration page by comparing them with the IMP and NIMP that have been retrieved and the patient treatment log forms. Reconciliation will occur with paper and electronic diary as appropriate depending on study visit/period.

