### 10.4.1.3 Adverse event of special interest

An adverse event of special interest (AESI) is an AE (serious or non-serious) of scientific and medical concern specific to the Sponsor's product or program, for which ongoing monitoring and immediate notification by the Investigator to the Sponsor is required. Such events may require further investigation in order to characterize and understand them. Adverse events of special interest may be added or removed during a study by protocol amendment.

For these AESIs, the Sponsor will be informed immediately (ie, within 24 hours), per SAE notification described [Section 10.4.4](#), even if not fulfilling a seriousness criterion.

AESIs for this study include:

- Anaphylactic or systemic allergic reactions that are related to IMP and that require treatment (refer to [Appendix H](#) for the definition of anaphylaxis).
- Severe injection site reactions that last longer than 24 hours.
- Any infection meeting at least 1 of the following criteria:
  - Any serious infection (SAE),
  - Requires parenteral (IV, IM, SC) antimicrobial therapy,
  - Requires oral antimicrobial therapy for longer than 2 weeks,
  - Is a parasitic infection,
  - Is an opportunistic infection (refer to [Appendix I](#)).

**Note:** Antimicrobial therapy refers to antibiotic, antiviral, and antifungal agents.

- Significant elevation of ALT.
  - ALT  $>5 \times$  ULN in patients with baseline ALT  $\leq 2 \times$  ULN;
  - or
  - ALT  $>8 \times$  ULN if baseline ALT  $>2 \times$  ULN
- Pregnancy occurring in a female patient entered in the clinical trial or in a female partner of a male patient entered in the clinical trial. It will be qualified as an SAE only if it fulfills 1 of the seriousness criteria (see [Section 10.4.1.2](#)).
  - In the event of pregnancy in a female participant, IMP should be discontinued.
  - Follow-up of the pregnancy in a female participant or in a female partner of a male participant is mandatory until the outcome has been determined.
- Symptomatic overdose (serious or non-serious) with IMP/NIMP
  - An overdose (accidental or intentional) with the IMP/NIMP is an event suspected by the Investigator or spontaneously notified by the patient (not based on systematic syringes or pills count) and defined as at least twice the intended dose during an interval of less than 11 days. The circumstances (ie, accidental or intentional) should be clearly specified in the verbatim and symptoms, if any, entered on separate AE forms.

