Of note, asymptomatic overdose has to be reported as a standard AE.

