**Table 4 - Summary of adverse event reporting instructions**

Adverse event/laboratory abnormality		Reporting timeframe
Serious adverse event		Within 24 hours
Adverse Event (non-SAE, non-AES) a		Routine
Pregnancy b		Within 24 hours
Overdose	Symptomatic	Within 24 hours
	Asymptomatic	Routine
ALT elevation	ALT >5 ULN if baseline ALT is ≤2 ULN	Within 24 hours
	ALT >8 ULN if baseline ALT is >2 ULN	Within 24 hours
Anaphylactic or systemic allergic reactions that are related to IMP and that require treatment		Within 24 hours
Severe injection site reactions that last longer than 24 hours		Within 24 hours
Infections as defined in Section 10.4.1.3		

ALT=alanine aminotransaminase; ULN=upper limit of normal.

*a* For reporting of epistaxis as an AE, use both AE form and Safety complementary form to provide date, features and outcome of the event.

*b* The drug exposure via parent form is not part of the Case Report Form, but needs to be completed for pregnancy

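### SAP 2.4.3.2 makes every IMP overdose a serious adverse event, contrary to protocol 10.4.1.3 and Table 4

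*SAP*

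**What the plan says.** SAP 2.4.3.2 (Compliance) falls under the heading for IMP exposure and compliance. After defining percentage compliance it states: "Cases of overdose (defined as at least twice the intended dose during an interval of less than 11 days) will constitute serious adverse events". The same sentence says they will be listed as such, and the next one sends dosing irregularities in general to a listing under SAP 2.2.1.

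Protocol 10.4.1.3 includes among the adverse events of special interest (AESI): "Symptomatic overdose (serious or non-serious) with IMP/NIMP". It defines an overdose with the same threshold of twice the intended dose in under 11 days, but adds that it "is an event suspected by the Investigator or spontaneously notified by the patient (not based on systematic syringes or pills count"). The section closes by saying that "asymptomatic overdose has to be reported as a standard AE".

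Protocol Table 4 sets reporting timeframes. Symptomatic overdose is due within 24 hours. Asymptomatic overdose is routine, the timeframe also given to events that are neither SAEs nor AESIs. SAEs are due within 24 hours.

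**The concern.** Seriousness is a defined property of an adverse event. Protocol 10.4.1.2 ties it to outcome criteria or medical importance, and under protocol 10.4.4 the investigator or a designee enters SAE information in the e-CRF. The SAP sentence assigns seriousness by rule to a whole class of events, part of which the protocol says need not be serious and part of which it calls ordinary AEs.

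What is at stake is the SAE listing. A programmer following SAP 2.4.3.2 literally would list as serious an overdose that the investigator recorded as non-serious. The listing would then disagree with the e-CRF and mix dosing events with events that meet the protocol's seriousness criteria.

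**Working it through.** No figure in the plan needs reproducing, so the check is a comparison of texts.

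**Step 1. Classification by kind of overdose**

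| Kind of IMP overdose | Protocol 10.4.1.3 | Protocol Table 4 | SAP 2.4.3.2 | Agree? |
|---|---|---|---|---|
| Symptomatic, meets a seriousness criterion | AESI, serious | Within 24 hours | SAE | Yes |
| Symptomatic, meets none | AESI, non-serious | Within 24 hours | SAE | No |
| Asymptomatic | Standard AE | Routine | SAE | No |

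The documents agree for one kind and conflict for two.

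**Step 2. Does the 24-hour timeframe imply seriousness?** No. Protocol 10.4.1.3 applies immediate notification to every AESI, including those that meet no seriousness criterion. Table 4 itself sets timeframes, not seriousness. It supports the contradiction only through the asymptomatic row, because an SAE could not carry the routine timeframe.

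**Step 3. Is overdose serious by definition elsewhere in the protocol?** Protocol 10.4.1.2 does not name overdose among the seriousness criteria or the examples of medically important events. The example list is stated not to be exhaustive, so an individual overdose could still be judged serious. That is a case-by-case judgement and does not support a blanket rule.

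**Step 4. Does the SAP declare or explain a change?** SAP 1.5 reports no change from the protocol's statistical section. Protocol 11.4.1.2, the compliance part of that section, summarises above-planned dosing descriptively and says nothing about SAEs. The overdose definition is in protocol section 10, which SAP 1.5 does not address. Nothing there accounts for the difference.

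**Step 5. What does the rest of the SAP do?** Table 1 identifies symptomatic overdose from a question on the e-CRF adverse event page, with no serious status attached. For each AESI, SAP 2.4.5.1 counts patients with any such event separately from patients with a serious one. Those sections leave seriousness open; 2.4.3.2 does not.

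**Step 6. The definition.** The threshold is the same in both documents. The SAP's parenthesis leaves out the protocol's limit to events that the investigator suspects or the patient reports, as opposed to events found by systematic counting. Compliance is the one area where counting is the normal data source: under protocol 8.7.1 the investigator or designee "tracks treatment accountability/compliance by diary, and by counting the number of used and unused treatment kits and syringes". A reader of SAP 2.4.3.2 alone cannot tell whether the limit still applies.

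**The case against.** The best defence is that the sentence is harmless. It uses the protocol's term and repeats its threshold, so it may simply assume the protocol's definition. Seriousness is recorded in the e-CRF, and over-calling it could be seen as cautious. This does not remove the contradiction: the wording is unconditional, no other section qualifies it, and a listing that disagrees with the investigator's record is harder to interpret.

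The defence does succeed against several stronger readings that a reader might infer:

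- **That overdoses will be harvested from diaries and syringe counts.** SAP 2.4.3.2 does not say so. Its next sentence keeps dosing irregularities apart, and the only case-finding rule the SAP gives, in Table 1, relies on an e-CRF answer. The missing limit is an ambiguity, not a demonstrated change of ascertainment.
- **That overdose of the nasal spray has been overlooked.** The sentence is in an IMP section. SAP Table 1 has a separate row for symptomatic overdose with the non-investigational product, and the AESI summaries cover it.
- **That any two injections given too close together count as an overdose.** Protocol 8.1.4 says: "Every other week IMP administrations must be separated by at least 11 days". But a breach of that rule need not mean twice the dupilumab dose. After Week 24, Arm B alternates dupilumab with placebo, and Arm C receives only placebo.
- **That SAE incidence tables will be inflated.** That would require seriousness to be derived by program from SAP 2.4.3.2, and no section calls for this.

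**Conclusion.** The contradiction on seriousness stands. SAP 2.4.3.2 classes all IMP overdoses as SAEs, while protocol 10.4.1.3 and Table 4 do not do so for symptomatic non-serious or asymptomatic overdoses. This is a rule that is wrong as written, not a missing detail.

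The size is minor. Any non-serious IMP overdose would be mislabelled in the SAE listing, assuming the sentence is applied literally. The documents give no expected number of such events, so none is stated. The incidence tables, efficacy results, type I error and power are not shown to be affected.

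The missing ascertainment limit is secondary. It is worth clarifying in the same edit, but it does not establish that record-only deviations would be listed as overdoses.

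**What to change.** Reconcile SAP 2.4.3.2 with protocol 10.4.1.3 and Table 4 by replacing the overdose sentence with text along these lines:

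> Overdoses with IMP as defined in protocol 10.4.1.3 will be listed, with seriousness as recorded by the investigator. Symptomatic overdoses are summarised as AESI (Table 1) and asymptomatic overdoses as AEs. Other dosing deviations are listed as dosing irregularities.

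This removes the blanket classification, and referring to the protocol definition restores the limit on ascertainment. The cost is a one-sentence SAP edit. The e-CRF question on symptomatic IMP overdose and the dosing-irregularity listing are already in the SAP, so no new data or analysis is needed.
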